Among the symptoms frequently associated with fibromyalgia, gastrointestinal symptoms are very common. In fact, in the specific case of one of the comorbid pathologies of fibromyalgia, irritable bowel syndrome (IBS), the prevalence of fibromyalgia has been estimated to range from 20 to 65% with a mean value of 41%.² On the other hand, even among patients with fibromyalgia who do not meet criteria to diagnose IBS, the presence of gastrointestinal symptomatology is frequently observed.⁷ The cause of these symptoms is unknown although in two previous publications it was suggested that they could be due to intestinal bacterial overgrowth.⁸⁻⁹ An unpublished study by our team found that, in comparison with controls, patients with fibromyalgia presented a clear alteration of the intestinal fermentation processes, although it could not be affirmed that this was due to bacterial overgrowth or other type of intestinal dysbiosis. A very recent study in patients with chronic fatigue syndrome, a pathology that shows a broad overlap with fibromyalgia, has found the presence of intestinal dysbiosis in these patients.¹⁰

No specific treatment has been studied to alleviate the gastrointestinal symptoms associated with fibromyalgia despite their frequency and their being mentioned by most of the patients as extremely annoying. This may explain the frequency with which these patients resort to diets of one type or another even though their benefits have not been demonstrated previously.¹¹ In this regard, the use of probiotics, alone or associated with prebiotics (synbiotics), could be an interesting therapeutic approach since the use of these products is advocated as an important alternative for the treatment of chronic pathologies of the gastrointestinal tract.¹¹⁻¹²

More concretely, the use of probiotics on the management of IBS has been recently revised in a metanalysis that found that the use of these products is effective to improve the symptoms of IBS, although more information is required to assess which individual species and strains are the most effective¹³. Among the different probiotics tested VSL#3 has shown some promising results in the treatment of IBS both in adults and in children¹⁴⁻¹⁶. VSL#3 is a polymicrobial probiotic combination product that includes multiple strains of three lyophilized bacteria species: *bifidobacterium*, *lactobacillus*, and *streptococcus*. It is available in sachets containing 450 billions of bacteria in powder form.

Considering both the frequency of comorbidity between fibromyalgia and IBS, as well as the frequent presence of non-specific gastrointestinal symptoms in patients with fibromyalgia who might be susceptible to be treated with probiotics, the objective of this trial is to assess the efficacy and tolerability of VSL#3 in patients with fibromyalgia and gastrointestinal symptomatology.

SUBJECTS AND METHODS

Inclusion criteria:

- To have been diagnosed with fibromyalgia, diagnosis that will be confirmed at the time of beginning the screening of patients using the ACR 2016 criteria (Wolfe 2016)
- 18 years of age or older.

- Agreement to voluntarily participate in the study by signing informed consent.
- Be willing to, and do not need under medical criteria, to modify the treatment previously received for fibromyalgia, both of pharmacological and non-pharmacological type, and not change the habits of life, especially about the habitual diet, during the trial's duration
- To regularly suffer (two or more times by week) from three or more of the following symptoms: abdominal pain, abdominal bloating, meteorism, flatulence, nausea, dyspepsia, eructation, constipation and/or diarrhea.

Exclusion criteria:

- To suffer severe mental illness other than major depression.
- To suffer severe renal, hepatic or cardiovascular organic disease that, at the discretion of the investigator, could interfere the participation in the study.
- To suffer any chronic gastrointestinal disease other than irritable bowel syndrome such as inflammatory bowel disease, active gastroduodenal ulcer or colorectal carcinoma.
- Pregnancy or breastfeeding.

Outcome variables:

The severity of the following types of gastrointestinal symptoms: abdominal pain, abdominal bloating, meteorism, flatulence, constipation, diarrhea, nausea, eructation, and dyspepsia will be evaluated using a Visual Analogue Scale (VAS).

The primary endpoint will be the mean severity of the three main gastrointestinal symptoms reported by patients with fibromyalgia, i.e. abdominal pain, abdominal bloating and meteorism.

A seven points, Likert-type scale, the Patient Global Improvement Scale (PGI) will be used to assess the relief of patients' general symptomatology.

Fibromyalgia Impact Questionnaire Revised (FIQR). This instrument was created to assess the overall symptoms related to fibromyalgia,¹⁷ a modified version having been created in 2009;¹⁸ the validated Spanish version will be used.¹⁹ The total score of the FIQR, assessed through various visual analogue scales, ranges from 0 to 100, and the higher the score, the greater the severity of fibromyalgia. It will allow checking whether an eventual improvement in the gastrointestinal symptoms is reflected in a smaller impact of the symptomatology associated with fibromyalgia.

Insomnia Severity Inventory (ISI). It is a brief questionnaire, composed of seven items evaluated on Likert-type scales, which allows assessing the severity of insomnia. Its total score can range from 0 to 28 points; the higher the score obtained, the greater the severity of insomnia. Since poor sleep quality is also a symptom frequently associated with fibromyalgia it will be used to check whether an eventual improvement in gastrointestinal symptoms is reflected in a better quality of sleep. The validated Spanish version of the questionnaire will be used.²⁰

9-item Patient Health Questionnaire (PHQ-9). It is a brief questionnaire whose objective is to evaluate depressive symptoms. It consists of 9 items evaluated using Likert-type scales. Its total score ranges from 0 to 27 points: the higher the score reached, the greater the severity of the depression. Since depression is also a symptom frequently associated with fibromyalgia it will be used to check whether an eventual improvement in gastrointestinal symptoms is reflected in an improvement in depressive symptomatology. A validated Spanish version of the questionnaire will be used.²⁰

Short-Form Health Survey SF-36. It is multi-item generic health survey intended to evaluate general health concepts not specific to any age, disease or treatment group. It measures 8 health domains: physical functioning, role physical, bodily pain, general health, vitality, social functioning, role emotional and mental health that can also be condensed in two summary measures: the Physical Component Summary (PCS) and the Mental Component Summary (MCS). The validated Spanish version will be applied²⁴.

Study development:

The period between the initial recruitment of patients and their entry into the trial will be two weeks; during this period, the subjects' suitability to be included in the study will be assessed.

The treatment will consist of the intake of 1 sachet of VSL#3 or matching placebo twice a day during 12 weeks. The assignment of the subjects to the group that will receive the active product or the placebo will be randomized.

On the day of initiation of treatment, the following questionnaires will be administered: VAS of abdominal pain, abdominal bloating, meteorism, flatulence, constipation, diarrhea, nausea, eructation and dyspepsia, FIQR, ISI, PHQ-9, PGI and SF-36.

VAS of gastrointestinal symptomatology will be filled weekly by the patients during the first 4 weeks of the trial and every 2 weeks between weeks 4 and 12 of the trial. At week 12, FIQR, ISI, PHQ-9 and quality of life questionnaire will also be completed again. PGI will be filled on weeks 4, 8, and 12.

At the end of the treatment period, patients will be monitored at 4, 12 and 24 weeks thereafter; these visits will measure VASs of gastrointestinal symptoms, FIQR, PGI and SF-36.

Adverse effects potentially associated with treatment will be collected at each visit through an open question system. Also, during the 12 weeks of treatment the medication packages will be collected to control therapeutic compliance.

Calculation of sample size and assessment of results

Given the absence of previous intervention studies in this area and, in general, limited information on this aspect of fibromyalgia, this should be considered a pilot study. To this consideration should be added the limitation as to the recruitment of patients by the participating sites. Thus, the calculation of the sample size is based on the feasibility of recruiting them. The recruitment of 120 patients has been estimated as a reasonable attainable goal.

The results obtained will be analyzed by applying the Student t test for independent samples to compare the data between the subjects who received placebo and those who received active product and with a two-way analysis of variance to compare the data in the subgroups of patients treated with placebo and with VSL#3..

References:

1. Clauw DJ. Fibromyalgia and related conditions. Mayo Clin Proc 2015; 90:680-692.
2. Yunus MB. The prevalence of fibromyalgia in other chronic pain conditions. Pain Res Treat 2012; 2012:584373.

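### The exclusion criteria do not address impaired immunity, so as written an immunosuppressed patient can be randomised to a 12-week course of a bacterial product or placebo

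*Combined protocol and SAP*

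**What the plan says.** The background describes the product: "VSL#3 is a polymicrobial probiotic combination product that includes multiple strains of three lyophilized bacteria species". On strength it says: "It is available in sachets containing 450 billions of bacteria in powder form". Under Study development, patients take "1 sachet of VSL#3 or matching placebo twice a day during 12 weeks".

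Under Subjects and methods, the exclusion list has four items:

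- Psychiatric illness of a severe kind, with major depression allowed.
- Organ disease, the only item that leaves a judgement to the site: "To suffer severe renal, hepatic or cardiovascular organic disease that, at the discretion of the investigator, could interfere the participation in the study".
- Chronic disease of the digestive tract, with irritable bowel syndrome allowed; three examples of excluded diseases are given, among them inflammatory bowel disease.
- Patients who are pregnant or who breastfeed.

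The inclusion criteria require a confirmed fibromyalgia diagnosis, age 18 or over with no upper limit, consent, unchanged fibromyalgia treatment and habits, and regular gastrointestinal symptoms. Study development adds a two-week period before entry in which suitability for inclusion is assessed, without naming further criteria. Adverse effects potentially associated with treatment are collected at each visit by open question.

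**The concern.** The study product consists of bacteria taken by mouth in large number for 12 weeks. Whether a patient's immune defences are intact is an obvious eligibility question for such a product, and the criteria do not ask it. The protocol does use exclusions of a protective kind (severe organ disease, pregnancy or breastfeeding), so an immune criterion would fit its own approach.

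What is at stake is patient safety at entry and consistency between sites. The protocol speaks of participating sites in the plural. If the decision on an immunosuppressed candidate rests on unwritten judgement, two sites may decide differently. Tolerability is part of the stated objective, and the protocol names no infection-specific monitoring, so the entry criteria are the main written protection on this point.

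**Working it through.** **Step 1. Does any criterion cover immune status?** Each clause that might do so, set against an immunosuppressed candidate:

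| Clause | What it covers | Would it exclude on immune status? |
|---|---|---|
| Exclusion: mental illness | Severe mental illness other than major depression | No |
| Exclusion: organ disease | Severe renal, hepatic or cardiovascular disease judged able to interfere with participation | No; the discretion is tied to these three organ systems |
| Exclusion: gastrointestinal disease | Chronic gastrointestinal disease other than irritable bowel syndrome | No; it removes some treated patients, for example those with inflammatory bowel disease, but because of the bowel disease |
| Exclusion: pregnancy | Pregnancy or breastfeeding | No |
| Inclusion: unchanged treatment | Treatment previously received for fibromyalgia, and habits such as diet | No; an immunosuppressant taken for another disease is not restricted |
| Two-week period before entry | Suitability for inclusion | No criterion stated |

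Colorectal carcinoma is the only cancer named, and it appears as an example of gastrointestinal disease. There is no general clause for other conditions that an investigator considers unsuitable. A patient who takes an immunosuppressant for, say, a non-gastrointestinal autoimmune disease therefore meets no exclusion on that ground.

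**Step 2. Exposure in the active arm.** The plan states no daily or total count, so there is no figure of its own to reproduce. The inputs are 450 billion bacteria per sachet (background), and 1 sachet twice a day for 12 weeks (Study development).

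- Per day: 450 billion x 2 = 900 billion.
- Days: 12 x 7 = 84.
- Sachets: 2 x 84 = 168.
- Total: 900 billion x 84 = 75,600 billion, or 75.6 trillion.

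These figures apply only to patients randomised to VSL#3. They take the one strength given in the background as the strength of the trial sachet. They describe exposure and are not a measure of risk.

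**Step 3. How many patients, and what risk?** The documents give no prevalence of immunosuppression among fibromyalgia patients, no infection rate on the product, and no allocation ratio. Neither an expected number of affected patients nor an expected number of events can be derived from them.

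**The case against.** The strongest reply is that the hazard itself is not in the documents. They report no infection, warning or contraindication for this product. They describe promising results in irritable bowel syndrome in adults and children, and nothing on this point contradicts itself. A bacterial count is not a probability of harm. The trial is by its own account a pilot sized on feasibility, and severely immunosuppressed patients are not the population it describes. A careful investigator could also decline such a patient during the two-week suitability assessment.

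Much of this stands, and it limits what may be claimed. A reader might infer several stronger things that the documents do not support:

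- *That a site would have no ground to refuse.* Suitability is assessed before entry, and meeting the listed criteria does not oblige an investigator to enrol. What holds is narrower: no written criterion supports refusal on immune status.
- *That the list guards only against hazards unrelated to a bacterial product and omits the one that is related.* The gastrointestinal exclusion concerns the organ to which the bacteria are delivered, and the protocol does not state the purpose of any exclusion.
- *That one serious infection would dominate the tolerability result.* No tolerability endpoint, threshold or analysis is defined, so this cannot be shown.
- *That a definite number of patients is exposed.* A share of 2 to 5% would give 0.02 x 120 = 2.4 to 0.05 x 120 = 6 candidates, but that share is a pure assumption and the point does not rest on it.

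The lack of any criterion on hypersensitivity to the product or placebo is a separate matter and adds nothing here.

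The reply does not remove the gap. The stated eligibility rule admits these patients, and an unspecified suitability step does not tell sites what to decide.

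**Conclusion.** The point holds as an eligibility gap. The exclusion criteria do not address impaired immunity, and the only discretion clause is confined to severe renal, hepatic or cardiovascular disease. As written, an immunosuppressed patient who meets the other criteria can be randomised to VSL#3, at 900 billion bacteria a day for 12 weeks, or to placebo.

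The size of any harm is unknown, because the documents give neither the infection risk nor the share of candidates affected. They do not support a claim that the trial exposes patients to a demonstrated hazard. The reason to act is that a plausible safety question is left unanswered in the entry rules and can be answered at almost no cost. It is a cheap improvement to the protocol and does not call the design or the analysis into question.

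The conclusion rests on two assumptions: that the printed exclusion list is complete, as it reads, and that the sachet strength in the background is that of the trial product.

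**What to change.** Add one exclusion criterion: known immunodeficiency or clinically significant immunosuppression, including current immunosuppressive treatment. Leave the exact definition and any thresholds to the investigators, and write them down before recruitment so that all sites apply the same rule. Ascertain it from the history and the medication list within the existing two-week period before entry. No new test or visit is needed, and the endpoints and analysis do not change.

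The cost is one line of text and a few lost candidates, probably mainly patients treated for an autoimmune comorbidity. The trial result will then not apply to the excluded group, and the report should say so. If the sponsor prefers to keep these patients eligible, the protocol should state that impaired immunity was considered and why no exclusion is made.

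### Baseline symptom severity is collected but not used in the primary comparison; adjusting for it costs nothing, and a second screening reading is only an optional addition to that.

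*Combined protocol and SAP*

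**What the plan says.** Under Study development in the combined protocol and SAP, two weeks separate recruitment from entry: "The period between the initial recruitment of patients and their entry into the trial will be two weeks". That window has one stated purpose: "during this period, the subjects' suitability to be included in the study will be assessed". No VAS is listed in it. The pre-treatment VAS comes at its end: "On the day of initiation of treatment, the following questionnaires will be administered: VAS of abdominal pain, abdominal bloating, meteorism", followed by the other symptoms and questionnaires. During treatment the form is completed often: "VAS of gastrointestinal symptomatology will be filled weekly by the patients during the first 4 weeks of the trial", then every two weeks to week 12. That gives eight readings, at weeks 1, 2, 3, 4, 6, 8, 10 and 12.

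Outcome variables defines the endpoint without a change score or a time point: "The primary endpoint will be the mean severity of the three main gastrointestinal symptoms reported by patients with fibromyalgia".

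The section on sample size and assessment of results gives the whole analysis. It begins "The results obtained will be analyzed by applying the Student t test for independent samples to compare the data between the subjects" and continues "with a two-way analysis of variance to compare the data in the subgroups of patients treated with placebo and with VSL#3". No covariate is named, and the subgroups are not defined. The target of 120 patients rests on recruitment feasibility.

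**The concern.** The sample size is limited by what the sites can recruit, so any gain in precision has to come from the same patients. Baseline severity usually predicts later severity on the same scale. A comparison that ignores it leaves that predictable part of the between-patient variation in the error term.

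The screening window raises a second, smaller question. Patients are already under assessment for two weeks before treatment, and a VAS taken then would give a second untreated reading. That reading is worth having only if the analysis uses baseline at all, so the two questions must be taken in that order. A pre-treatment reading cannot be recovered once treatment has started.

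**Working it through.** **Inputs from the documents.** Total 120 patients; one pre-treatment VAS set; t test with no stated covariate.

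**Assumptions, none given in the documents.** 1:1 allocation (60 per arm), no dropout, two-sided 5% level, 80% power, week 12 as the outcome time, and an illustrative effect of 0.4 SD. Here r is the correlation of the treatment-day reading with the outcome, r2 that of a screening reading with the outcome, and b the correlation between the two pre-treatment readings. The figure of 120 has no statistical inputs, so there is no calculation to reproduce.

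**Step 1: the analysis as written.** For a t test on post-treatment scores, the detectable difference is (1.96 + 0.84) × √(2/60) = 0.511 SD. Power for 0.4 SD is 0.591. Neither depends on how many baseline readings exist; the relative variance stays 1.00 with one or with two.

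**Step 2: adjust for the reading already planned.** The relative variance under ANCOVA is 1 − r². The detectable difference is 0.511 × √(1 − r²).

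| r | Relative variance | Detectable difference (SD) | Power for 0.4 SD |
|---|---|---|---|
| 0.3 | 0.91 | 0.488 | 0.632 |
| 0.5 | 0.75 | 0.443 | 0.716 |
| 0.7 | 0.51 | 0.365 | 0.866 |
| 0.8 | 0.36 | 0.307 | 0.955 |

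At r = 0.5 power rises by about 12 points. The precision equals that of an unadjusted comparison in 120/0.75 = 160 patients.

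**Step 3: add a screening reading, with r = 0.5.**
- Mean of the two as one covariate: 1 − (r + r2)²/[2(1 + b)].
- Both as separate covariates: 1 − (r² + r2² − 2·r·r2·b)/(1 − b²).

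Worked example with r2 = 0.45 and b = 0.7. The mean gives 1 − 0.9025/3.4 = 0.735. Separate covariates give 1 − (0.25 + 0.2025 − 0.315)/0.51 = 0.730.

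| r2 | b | Mean of two | Both as covariates | Further cut from 0.75 (both) |
|---|---|---|---|---|
| 0.50 | 0.50 | 0.667 | 0.667 | 11% |
| 0.50 | 0.70 | 0.706 | 0.706 | 6% |
| 0.50 | 0.80 | 0.722 | 0.722 | 4% |
| 0.45 | 0.70 | 0.735 | 0.730 | 3% |
| 0.45 | 0.80 | 0.749 | 0.743 | 1% |
| 0.445 | 0.891 | 0.764 | 0.750 | 0% |

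The last row is exponential decay of correlation with time, set to 0.5 at 12 weeks. A screening reading is then 14 weeks from the outcome (0.5^(14/12) = 0.445) and 2 weeks from the other baseline (0.5^(2/12) = 0.891). In that row the simple mean does worse than one reading (0.764 against 0.750), while separate covariates break even.

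The top row corresponds to 120 × 0.75/0.667 − 120 = 15 extra patients, and power for 0.4 SD goes from 0.716 to 0.765. It requires readings 2 weeks apart to correlate no better than readings 12 weeks apart, so it is the optimistic end.

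**Check.** In 5,000 simulated trials with all correlations 0.5, the relative variances were 0.98 (unadjusted), 0.74 (one reading) and 0.65 (mean of two), against theory of 1, 0.75 and 0.667.

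**The case against.** The strongest reply is that one pre-treatment reading on the treatment day is ordinary practice, contradicts nothing in the documents, and suits a trial that calls itself a pilot. That stands. A reader might infer that the trial loses precision because baseline is read only once. The documents do not support this: no baseline-adjusted comparison is planned, and under the t test as written a second reading changes nothing.

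A reader might also infer that the single reading is an unreliable one-day score. The VAS recall period is not stated, and weekly completion is equally compatible with a past-week rating. The entry rule of symptoms at least twice a week is a minimum frequency, not evidence of how much severity scores vary.

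Nor may a gain from the second reading be taken for granted. A guaranteed gain would need the older reading to predict the outcome as well as the newer one, and the documents give no correlations to show that.

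It could be argued that the t test is meant for change scores, or that the two-way analysis of variance includes baseline. The text says neither. If change scores were used, the relative variance would be 2(1 − r), which is 1.00 at r = 0.5 and 1.40 at r = 0.3. ANCOVA, at 0.75 and 0.91, does better in both cases. A second reading would then help without ANCOVA: with all correlations 0.5, averaging two readings takes 1.00 to 0.75.

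**Conclusion.** The point holds as a missed opportunity, not as an error: in a randomised trial the unadjusted t test is unbiased. The main gap is that a baseline composite is collected and then not used. Adjusting for it leaves 0.91 to 0.36 of the unadjusted variance for correlations of 0.3 to 0.8, and 0.75 at 0.5. The second reading is secondary. At r = 0.5 it cuts the remaining variance by about 0 to 11%, and averaging the two readings can even lose a little. All these sizes rest on assumed correlations, and the power figures also on the assumed 1:1 allocation, full retention, test level and effect size. That adjustment is worth making does not depend on the exact values, since 1 − r² falls below 1 for any non-zero correlation, apart from the loss of one of about 118 residual degrees of freedom.

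**What to change.** Replace the t test for the primary composite by ANCOVA with treatment group and the baseline composite (mean of abdominal pain, bloating and meteorism on the treatment day), at a named time point. This uses data already planned and costs nothing beyond a sentence in the analysis section.

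Optionally, and only together with that change, have patients complete the VAS set at the start of the two-week screening period as well. Enter the two pre-treatment composites as separate covariates rather than their mean, so that an older, less predictive reading cannot pull the adjustment down; the price is one further degree of freedom. State in advance that where a patient has only one reading, that reading is used. The cost is one extra form per screened patient, some of them from people who are never randomised. This choice has to be made before enrolment starts.

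### Several sites recruit, but site appears in neither the assignment nor the between-arm comparison: a small loss of precision that is cheap to avoid

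*Combined protocol and SAP*

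**What the plan says.** Under Study development, allocation has one sentence: "The assignment of the subjects to the group that will receive the active product or the placebo will be randomized". The text gives no ratio, sequence type, blocking, stratification or concealment.

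Under Calculation of sample size and assessment of results, the protocol cites "the limitation as to the recruitment of patients by the participating sites", so more than one site recruits; their number and sizes are not stated. On size it says "the calculation of the sample size is based on the feasibility of recruiting them" and "The recruitment of 120 patients has been estimated as a reasonable attainable goal".

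The analysis consists of "applying the Student t test for independent samples to compare the data between the subjects who received placebo and those who received active product", together "with a two-way analysis of variance to compare the data in the subgroups of patients treated with placebo and with VSL#3". The factors of that analysis of variance are not named. The Outcome variables section defines the endpoint: "The primary endpoint will be the mean severity of the three main gastrointestinal symptoms reported by patients with fibromyalgia", each scored on a VAS that, according to Study development, patients fill in.

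**The concern.** Site is a plausible source of variation in a self-rated symptom score, because case mix and the way the scale is explained may differ between centres. The protocol does not say that they do, so this is an assumption.

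Two things follow if site is left out of both design and analysis. First, unless allocation is balanced within site, one site can by chance contribute more patients to one arm, and any site difference then enters the VSL#3 versus placebo contrast in that trial. Second, the t test leaves between-site variance in its error term.

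Sample size was set by feasibility, so lost precision cannot easily be recovered by adding patients.

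**Working it through.** **Inputs from the protocol.** Total 120; several sites; allocation described only as randomised; independent-samples t test. The 120 cannot be reproduced by a power calculation, because no effect size, SD, alpha or power is given.

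**Assumed.** 1:1 allocation (60 per arm), two-sided alpha 0.05, total SD 1, true effect 0.5 SD, equal-sized sites, and a site share of outcome variance ρ of 0.02 to 0.10, with 0.20 as an extreme.

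**1. Chance imbalance within a site.** The method is not stated, so two readings are shown. Simple randomisation uses two-sided binomial tails at 0.5. Fixing only the overall 60:60 total uses the hypergeometric distribution.

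| Site size | Split or worse | Simple | Overall 60:60 fixed |
|---|---|---|---|
| 30 (4 sites) | 10:20 | 9.9% | 5.7% |
| 40 (3 sites) | 14:26 | 8.1% | 3.3% |
| 60 (2 sites) | 23:37 | 9.2% | 1.7% |

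Under simple randomisation, the chance that at least one of four sites of 30 is split this badly is 1 − (1 − 0.099)^4 = 34%.

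**2. What a split does to the contrast.**
- Four sites of 30, one split 10:20 and the others even, so the arms are 55 and 65. That site makes up 10/55 = 0.182 of one arm and 20/65 = 0.308 of the other, a difference of 0.126. If it differs from the rest by one between-site SD (√ρ), the contrast shifts by 0.126 × √0.05 = 0.03 SD or 0.126 × √0.10 = 0.04 SD. The standard error is √(1/55 + 1/65) = 0.18 SD.
- Two sites of 60, each split 36:24 in opposite directions. The site difference is 2√ρ and the shift is (0.6 − 0.4) × 2√ρ, which is 0.09 SD at ρ = 0.05 and 0.13 SD at ρ = 0.10. With the overall total fixed, a split this bad or worse has probability 4.4%.

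**3. Precision.** Without site, SE = √(2/60) = 0.1826. With site, SE ≈ √(1 − ρ) × 0.1826. Power ≈ Φ(0.5/SE − 1.96).

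| ρ | SE | Reduction in SE | Power |
|---|---|---|---|
| no site term | 0.1826 | – | 78.2% |
| 0.02 | 0.1807 | 1.0% | 79.0% |
| 0.05 | 0.1780 | 2.5% | 80.2% |
| 0.10 | 0.1732 | 5.1% | 82.3% |

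The gain is 0.8 to 4.1 points. At the extreme of ρ = 0.20, power would be 86.5%.

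**4. Type I error.** This was simulated with 20,000 runs per setting, 2, 4 or 6 equal sites, 60 per arm overall, and ρ of 0.05, 0.10 and 0.20.
- Unstratified allocation, plain t test: 4.8% to 5.1%.
- Stratified by site, plain t test: 4.3% to 4.6% at ρ = 0.05, 3.9% to 4.1% at 0.10 and 2.8% at 0.20, so conservative.
- Stratified by site, site in the model: 4.7% to 5.2%.
- Two sites, unstratified, among only those runs split 36:24 or worse: about 8%, 11% and 16% at the three values of ρ.

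**The case against.** The strongest reply is that randomisation with an unadjusted t test is a valid analysis, and that a pilot sized on feasibility need not pursue the last few points of efficiency. Validity stands. A reader might infer that ignoring site raises the false-positive rate. The simulation does not support that: over repeated unstratified randomisations the rate stays near 5%. The 8% to 16% figures apply only after a two-site split that occurs about 4% of the time.

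A reader might also infer that the plan uses simple, unblocked randomisation. The text does not say so. It gives no method, and a randomisation list kept outside the protocol may be blocked or stratified. That is why both columns are shown in the first table. But such a list would not put site into the stated t test, and stratifying while ignoring site would make that test conservative.

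Nor should imbalance and error variance be counted as two separate losses. Under unstratified allocation, the between-site variance in the error term is what allows for chance imbalance. With equal splits the site differences cancel from the estimate, and the t test merely overstates its standard error.

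The two-way analysis of variance does not settle the matter, since its factors are unnamed. The pilot label reduces the weight of the point but does not remove it: the protocol sets out to assess efficacy, names a primary endpoint and tests it between arms.

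**Conclusion.** The point holds as a matter of efficiency, not validity. Several sites recruit, and site enters neither the described allocation nor the described analysis. If site explains 2% to 10% of VAS variance, leaving it out costs about 1 to 4 points of power at an effect of 0.5 SD with 60 per arm, and leaves the single trial open to modest shifts in the contrast from uneven splits within sites. The number of sites, the site share of variance, the effect size and the 1:1 ratio are all assumptions. This is a cheap improvement.

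**What to change.** State the allocation method: 1:1, in randomly permuted blocks of varying size within each site, from a centrally prepared list concealed from recruiting staff. For the primary endpoint, replace the plain t test with a linear model containing treatment and site. Make both changes together, because stratifying without the site term gives a conservative test. Set a rule for pooling very small sites before unblinding, and name the factors of the two-way analysis of variance.

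The cost is a different computer-generated list, one model factor and a few degrees of freedom. No extra patients or visits are needed.
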